14. Excluded treatments during the study treatment period. Subject has to take one of the following drugs that are listed in [Table 1](#) during the study.

Table 1 Prohibited Medications Prior to Start of Study Treatment and During Study Treatment

Prohibited Medications Prior to Start of Study Treatment and During Study Treatment	Washout Period ^a
Systemic antifungal therapy (oral, intravenous or inhaled) other than study drugs for reasons other than antifungal prophylaxis.	30 days
Investigational drugs (new chemical or biological entities): Investigational use of approved products or chemotherapy regimens may be permitted with the approval of the sponsor's project physician prior to use.	30 days
Prophylaxis of IFI with posaconazole.	10 days
Medications that are known to interact with azoles and may lead to life-threatening side effects: astemizole, cisapride, ebastine, halofantrine, pimozide, quinidine, and terfenadine.	10 days (astemizole) 24 hours (others)
Ergot alkaloids (ergotamine, dihydroergotamine or other licensed or investigational members of this class).	2 days
Medications known to lower the serum concentration/efficacy of azole antifungals: barbiturates, carbamazepine, cimetidine, isoniazid, phenytoin, rifabutin, rifampin, and St. John's Wort (hypericum perforatum).	24 hours
Prophylactic use of nonabsorbable antifungal drugs: Nasal sprays of amphotericin B and aerosolized amphotericin B are prohibited.	24 hours
HMG-CoA reductase inhibitors metabolized via CYP3A4 (eg, simvastatin, lovastatin, and atorvastatin).	24 hours
Cyclophosphamide ^b	24 hours

a: These waiting times should be observed prior to start of study treatment and during study treatment in subjects receiving a prohibited drug. No concurrent use is permitted. Deviations from these washout periods must be approved by the sponsor prior to use of study drug or prohibited agent.

b: Low dose cyclophosphamide use is allowed during the treatment period with a temporary interruption of study therapy on the day of cyclophosphamide dosing.

HMG-CoA=beta-hydroxy-beta-methylglutaryl-CoA; IFI = invasive fungal infection

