7.1.1.5.2 Concomitant Medications

The investigator or qualified designee will record medication, if any, taken by the subject during the trial.

Nasal sprays of amphotericin B (AMB) and aerosolized AMB are prohibited during the Treatment Phase. Topical nonabsorbable antifungal agents may be used for the treatment of mucosal or cutaneous fungal infections. Any other antifungal therapy must be administered according to the following criteria. No other systemic antifungal therapy is allowed other than study treatment.

Investigational drugs (ie, other drugs not yet approved for marketing by the Food and Drug Administration [FDA] or local health authorities) are also prohibited during the treatment phase.

POS is a potent inhibitor of CYP3A4. Coadministration of POS with CYP3A4 substrates may result in large increases in exposure of CYP3A4 substrates. Caution is advised during co-administration of POS with CYP3A4 substrates and the dose of the CYP3A4 substrate may need to be reduced. Plasma concentrations of the CYP3A4 substrate and/or AEs should be closely monitored and the dose adjusted as needed.

Clinical and ECG monitoring (including QTc monitoring) is to be performed when the study drug is co-administered with one of the following drugs that have reported a potential risk of torsades de pointes: amiodarone, chlorpromazine, clarithromycin, domperidone, droperidol, levomethadyl, mesoridazine, methadone, erythromycin, sparfloxacin, and thioridazine.

The drugs listed below are permitted, although their efficacy and safety should be clinically monitored and/or serum levels followed with appropriate dosage adjustments as necessary at the initiation of study drug, periodically during treatment, and after discontinuation of study drug:

- Oral hypoglycemic agents
- Digoxin
- Coumadin-type anticoagulants
- Calcium channel blockers
- Theophylline
- Antiretroviral therapy (eg, efavirenz, atazanavir, or tenofovir).

Posaconazole interferes with the hepatic clearance of triazolam and midazolam, and thus, may enhance the sedative effects of these agents. Therefore, these agents are not allowed unless monitoring is provided for excessive sedation.

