8.2.3 Approaches to Analyses

The following populations are defined for the analysis and reporting of data. All subjects will be reported, and their data analyzed, according to the treatment(s) they actually received.

All Subjects as Treated (ASaT): All subjects who received at least one dose of the investigational drug. This population will be used for assessments of safety and tolerability.

Per-Protocol (PP) population: The set of data generated by the subset of subjects who comply with the protocol sufficiently to ensure that these data will be likely to exhibit the effects of treatment, according to the underlying scientific model. Compliance covers such considerations as exposure to treatment, availability of measurements and absence of major protocol deviations. Major protocol deviations will be identified to the extent possible prior to unblinding by individuals responsible for data collection/compliance, and its analysis and interpretation. Any subjects or data values excluded from analysis will be identified, along with their reason for exclusion, in the CSR. At the end of the study, all subjects who are compliant with the study procedure as aforementioned and have available data from at least one treatment will be included in the primary analysis dataset. This population will be used for the PK analysis.

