There is no information regarding cross-sensitivity between posaconazole and other azole antifungal agents. Caution should be used when prescribing Noxafil to patients with hypersensitivity to other azoles.

Gastrointestinal dysfunction

There are limited pharmacokinetic data in patients with severe gastrointestinal dysfunction (such as severe diarrhoea). Patients who have severe diarrhoea or vomiting should be monitored closely for breakthrough fungal infections.

Rifamycin antibiotics (rifampicin, rifabutin), certain anticonvulsants (phenytoin, carbamazepine, phenobarbital, primidone), efavirenz and cimetidine

Posaconazole concentrations may be significantly lowered in combination; therefore, concomitant use with posaconazole should be avoided unless the benefit to the patient outweighs the risk.

Excipients

This medicinal product contains approximately 1.75 g of glucose per 5 ml of suspension. Patients with glucose-galactose malabsorption should not take this medicine.

Effects on ability to drive and use machines

No studies on the effects of posaconazole on the ability to drive and use machines have been performed. Since certain adverse reactions (e.g. dizziness, somnolence, etc.) have been reported with posaconazole use, which potentially may affect driving/operating machinery, caution needs to be used.

[Pregnancy & Nursing Mothers]

Pregnancy Category C:

There are no adequate and well-controlled studies in pregnant women. NOXAFIL should be used in pregnancy only if the potential benefit outweighs the potential risk to the fetus.

Posaconazole has been shown to cause skeletal malformations (cranial malformations and missing ribs) in rats when given in doses ≥ 27 mg/kg (≥ 1.4 times the 400-mg BID regimen based on steady-

state plasma concentrations of drug in healthy volunteers). The no-effect dose for malformations in rats was 9 mg/kg, which is 0.7 times the exposure achieved with the 400-mg BID regimen. No malformations were seen in rabbits at doses up to 80 mg/kg. In the rabbit, the no-effect dose was 20 mg/kg, while high doses of 40 mg/kg and 80 mg/kg, 2.9 or 5.2 times the exposure achieved with the 400-mg BID regimen, caused an increase in resorptions. In rabbits dosed at 80 mg/kg, a reduction in body weight gain of females and a reduction in litter size were seen.

Nursing Mothers

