Efavirenz: Efavirenz induces UDP-glucuronidase and significantly decreases posaconazole plasma concentrations. 400mg once a day decreased the Cmax and AUC of posaconazole by 45% and 50%, respectively. It is recommended to avoid concomitant use of efavirenz with posaconazole unless the benefit outweighs the risks.

Ritonavir and Atazanavir: Ritonavir and atazanavir are metabolized by CYP3A4 and posaconazole increases plasma concentrations of these drugs. Frequent monitoring of adverse effects and toxicity of ritonavir and atazanavir should be performed during coadministration with posaconazole.

Fosamprenavir: Combining fosamprenavir with posaconazole may lead to decreased posaconazole plasma concentrations. If concomitant administration is required, close monitoring for breakthrough fungal infections is recommended. Repeat dose administration of fosamprenavir (700 mg BID x 10 days) decreased the C_{max} and AUC of posaconazole (200 mg oral suspension QD on the 1st day, 200 mg oral suspension BID on the 2nd day, then 400 mg oral suspension BID x 8 Days) by 21% and 23%, respectively.

7. Rifabutin

Rifabutin induces UDP-glucuronidase, Rifabutin 300mg once a day decreased the C_{max} and AUC of posaconazole by 43% and 49%, respectively. Rifabutin is also metabolized by CYP3A4. Therefore, coadministration of rifabutin with posaconazole increases the Cmax and AUC of rifabutin by 31% and 72%, respectively. Concomitant use of posaconazole and rifabutin should be avoided unless the

benefit to the patient outweighs the risk. However, if concomitant administration is required, close monitoring for breakthrough fungal infections as well as frequent monitoring of full blood counts and adverse reactions due to increased rifabutin plasma concentrations (e.g., uveitis, leukopenia) are recommended.

8. Phenytoin

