Phenytoin induces UDP-glucuronidase. Phenytoin 200mg once a day decreased the C_{max} and AUC of posaconazole by 41% and 50%, respectively. Phenytoin is also metabolized by CYP3A4. Therefore, coadministration of phenytoin with posaconazole increases phenytoin plasma concentrations. Concomitant use of posaconazole and phenytoin should be avoided unless the benefit to the patient outweighs the risk. However, if concomitant administration is required, close monitoring for breakthrough fungal infections is recommended and frequent monitoring of phenytoin concentrations should be performed while coadministered with posaconazole and dose reduction of phenytoin should be considered.

9. Gastric Acid Suppressors/Neutralizers

Cimetidine (an H2-receptor antagonist) and esomeprazole (a proton pump inhibitor) decrease posaconazole plasma concentrations. It is recommended to avoid concomitant use of cimetidine and esomeprazole with posaconazole unless the benefit outweighs the risks.

Posaconazole plasma concentrations (C_{max} and AUC) were reduced by 39 % when posaconazole oral suspension was administered with cimetidine (400 mg twice a day) due to reduced absorption possibly secondary to a decrease in gastric acid production. Co-administration of posaconazole oral suspension with H2 receptor antagonists should be avoided if possible.

Similarly, administration of 400 mg posaconazole oral suspension with esomeprazole (40 mg daily) decreased mean C_{max} and AUC by 46 % and 32 %, respectively, compared to dosing with 400 mg posaconazole alone. Co-administration of posaconazole oral suspension with proton pump inhibitors should be avoided if possible.

However, if concomitant administration is required, close monitoring for breakthrough fungal infections is recommended. No clinically relevant effects were observed when posaconazole is concomitantly used with antacids and H2-receptor antagonists other than cimetidine. No dosage adjustment of posaconazole is required when posaconazole is concomitantly used with antacids and H2 receptor antagonists other than cimetidine.

10. Vinca Alkaloids

Most of the vinca alkaloids are substrates of CYP3A4. Posaconazole may increase the plasma concentrations of vinca alkaloids (e.g., vincristine and vinblastine) which may lead to neurotoxicity. Therefore, it is recommended that dose adjustment of the vinca alkaloid be considered.

11. Calcium Channel Blockers Metabolized by CYP3A4

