Posaconazole primarily circulates as the parent compound in plasma. Of the circulating metabolites, the majority are glucuronide conjugates formed via UDP glucuronidation (phase 2 enzymes). Posaconazole does not have any major circulating oxidative (CYP450 mediated) metabolites. The excreted metabolites in urine and feces account for ~17% of the administered radiolabeled dose.

Posaconazole is primarily metabolized via UDP glucuronidation (phase 2 enzymes) and is a substrate for p-glycoprotein (P-gp) efflux. Therefore, inhibitors or inducers of these clearance pathways may affect posaconazole plasma concentrations. A summary of drugs studied clinically, which affect posaconazole concentrations, is provided in Table 12.

TABLE 12: Summary of the Effect of Coadministered Drugs on Posaconazole in Healthy Volunteers

Coadministered Drug (Postulated Mechanism of Interaction)	Coadministered Drug Dose/Schedule	Posaconazole Dose/Schedule	Effect on Bioavailability of Posaconazole	
			Change in Mean C_{max} (ratio estimate*; 90% CI of the ratio estimate)	Change in Mean AUC (ratio estimate*; 90% CI of the ratio estimate)
Efavirenz (UDP-G Induction)	400 mg QD × 10 and 20 days	400 mg (oral suspension) BID × 10 and 20 days	↓ 45% (0.55; 0.47-0.66)	↓ 50% (0.50; 0.43-0.60)
Fosamprenavir (unknown mechanism)	700 mg BID x 10 days	200 mg QD on the 1st day, 200 mg BID on the 2nd day, then 400 mg BID x 8 Days	↓ 21% 0.79 (0.71-0.89)	↓ 23% 0.77 (0.68-0.87)
Rifabutin (UDP-G Induction)	300 mg QD x 17 days	200 mg (tablets) QD × 10 days	↓ 43% (0.57; 0.43-0.75)	↓ 49% (0.51; 0.37-0.71)
Phenytoin (UDP-G Induction)	200 mg QD x 10 days	200 mg (tablets) QD × 10 days	↓ 41% (0.59; 0.44-0.79)	↓ 50% (0.50; 0.36-0.71)
Cimetidine (Alteration of Gastric pH)	400 mg BID × 10 days	200 mg (tablets) QD × 10 days	↓ 39% (0.61; 0.53-0.70)	↓ 39% (0.61; 0.54-0.69)
Esomeprazole (Increase in gastric pH)	40 mg QAM × 3 days	400 mg (oral suspension) single dose	↓ 46% (0.54; 0.43-0.69)	↓ 32% (0.68; 0.57-0.81)
Metoclopramide (Increase in gastric motility)	10 mg TID × 2 days	400 mg (oral suspension) single dose	↓ 21% (0.79; 0.72-0.87)	↓ 19% (0.81; 0.72-0.91)

* Ratio Estimate is the ratio of coadministered drug plus posaconazole to posaconazole alone for C_{max} or AUC.

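### Efavirenz is permitted by name, while Table 1 bans rifabutin and phenytoin, which lower posaconazole exposure about as much, by the same postulated mechanism and under the same conditional label advice

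*Combined protocol and SAP*

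**What the plan says.** Section 7.1.1.5.2 (Concomitant Medications) gives a list of permitted drugs that includes "Antiretroviral therapy (eg, efavirenz, atazanavir, or tenofovir". The condition attached to the list is that "their efficacy and safety should be clinically monitored and/or serum levels followed with appropriate dosage adjustments as necessary".

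Table 1 (Section 5.1.3) prohibits, before and during treatment, "Medications known to lower the serum concentration/efficacy of azole antifungals: barbiturates, carbamazepine, cimetidine, isoniazid, phenytoin, rifabutin, rifampin" and St. John's Wort, with a 24-hour washout. Footnote a bars concurrent use. Efavirenz is not listed.

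The oral suspension circular in Section 12.10 covers efavirenz in three places:
- **Precaution:** it is grouped under "Rifamycin antibiotics (rifampicin, rifabutin), certain anticonvulsants (phenytoin, carbamazepine, phenobarbital, primidone), efavirenz and cimetidine", with a warning that posaconazole concentrations may fall significantly.
- **Drug Interactions:** "It is recommended to avoid concomitant use of efavirenz with posaconazole unless the benefit outweighs the risks".
- **Table 12:** it appears as "Efavirenz (UDP-G Induction", the mechanism also given there for rifabutin and phenytoin.

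The circular's advice on phenytoin takes the same form: "Concomitant use of posaconazole and phenytoin should be avoided unless the benefit to the patient outweighs the risk". The advice on rifabutin is equivalent.

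**The concern.** Three drugs with the same postulated mechanism, nearly the same effect on posaconazole and the same conditional label advice get opposite treatment. Two are banned, one is allowed by name, and no reason is given.

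The monitoring condition does not close the gap. It suits drugs whose own levels posaconazole raises, such as digoxin, calcium channel blockers or atazanavir. Efavirenz acts in the other direction, and nothing in that sentence points to low posaconazole exposure. Section 7.1.5.5 does not allow the posaconazole dose to be changed, so the remedy would be to stop or replace efavirenz, and the permission gives no prompt to do so.

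Two things are at stake. The first is one neutropenic subject's prophylaxis: the circular says that lower average concentrations may go with a higher risk of treatment failure. The second is the primary parameter. Permitted use is not a protocol deviation, so an affected Day 10 profile would probably stay in the per-protocol Cavg summary and the population PK data.

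**Working it through.** **1. Side-by-side comparison (circular Table 12; protocol Table 1 and Section 7.1.1.5.2)**

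| Drug | Postulated mechanism | Posaconazole AUC ratio (90% CI) | Cmax ratio | Circular's advice | Protocol status |
|---|---|---|---|---|---|
| Efavirenz | UDP-G induction | 0.50 (0.43-0.60) | 0.55 | Avoid unless benefit outweighs risk | Permitted |
| Rifabutin | UDP-G induction | 0.51 (0.37-0.71) | 0.57 | Same | Prohibited |
| Phenytoin | UDP-G induction | 0.50 (0.36-0.71) | 0.59 | Same | Prohibited |

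The AUC ratios differ by at most 0.01 and the Cmax ratios by at most 0.04. The comparison stops at these two drugs. Cimetidine acts through gastric pH (AUC -39%), and the documents give no posaconazole effect size for the rest of that Table 1 row.

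**2. The plan's own figure.** Section 8.2.3.3 assumes mean Cavg 1,500 ng/mL and CV 35%, and states a probability above 90% that at least 18 of 20 evaluable subjects reach 500 ng/mL.
- Normal: SD = 0.35 x 1,500 = 525; z = (500 - 1,500)/525 = -1.90; P(<500) = 0.0284; binomial P(at least 18 of 20) = 0.982.
- Lognormal: sigma = sqrt(ln(1 + 0.35^2)) = 0.340; P(<500) = 0.0011; P(at least 18 of 20) > 0.9999.

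The stated figure is reproduced under both. The lognormal fits the earlier study better. None of its 49 subjects was below 500 ng/mL, which has probability (1 - 0.0011)^49 = 0.95 under the lognormal and (1 - 0.0284)^49 = 0.24 under the normal.

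**3. An exposed subject.** Cavg is AUC0-24 divided by the dosing interval, so an AUC ratio passes straight to Cavg. Assumptions: the oral ratio applies to IV dosing and the CV stays at 35%.

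| Ratio | Mean Cavg (ng/mL) | P(<500), normal | P(<500), lognormal |
|---|---|---|---|
| 1.00 | 1,500 | 0.028 | 0.001 |
| 0.60 | 900 | 0.102 | 0.059 |
| 0.50 | 750 | 0.170 | 0.153 |
| 0.43 | 645 | 0.260 | 0.281 |

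At ratio 0.50, letting the CV run from 25% to 50% gives 6% to 27%.

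**4. One exposed subject among the 20 evaluable**
- Mean shift = 1,500 x (1 - ratio)/20 = 37.5 ng/mL, or 2.5%, at ratio 0.50 (30 to 43 ng/mL, 2.0% to 2.9%, over the CI).
- Shift in the expected percentage at or above 500 ng/mL: (0.170 - 0.028)/20 = 0.7 points (normal) or (0.153 - 0.001)/20 = 0.8 points (lognormal).
- P(at least 18 of 20), normal: 0.970 at ratio 0.50 (0.976 at 0.60, 0.962 at 0.43). Lognormal: still above 0.9999.
- With two exposed at ratio 0.50: 0.953 (normal), 0.999 (lognormal). With three: 0.931 and 0.995.

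**5. Does anything else cancel the permission?** No criterion excludes HIV-positive subjects, and HIV testing follows site SOP. Inclusion 5 and exclusion 15 let an investigator keep such a subject out but do not require it. The local-label instruction in Sections 5.2 and 5.2.2 covers oral suspension, whereas the Day 10 profile is taken on IV dosing.

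**The case against.** The strongest reply has four parts.

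- **The advice is conditional.** A reader might infer that the circular forbids efavirenz and that the protocol contradicts it outright. It does not: a caution subject to benefit and risk can coexist with a monitored permission. It could also be argued that Table 1 is too strict on rifabutin and phenytoin. That stands, and the direction of harmonisation is a clinical judgement. The unequal treatment remains, because the same condition applies to the two banned drugs.
- **Safeguards exist.** The circular is part of the protocol and carries the caution twice. Signs and symptoms of fungal infection are checked at every treatment visit (Sections 6.0 and 7.1.2.5), and a possible, probable or proven infection requires discontinuation (Section 5.8). These rules address the clinical consequence. They do not prevent low exposure.
- **The size is conditional.** The 0.50 ratio comes from oral suspension 400 mg BID in healthy volunteers, while rifabutin and phenytoin were studied with tablets. No IV figure is given, and expected efavirenz use is not stated. This stands. Carry-over is plausible because the circular treats glucuronidation as a clearance pathway, but it is assumed.
- **Retention is not automatic.** Section 8.2.3 allows values to be left out, provided that "Any subjects or data values excluded from analysis will be identified, along with their reason for exclusion, in the CSR". This also stands, but no rule says when a profile taken under an inducer should be set aside.

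**Conclusion.** The inconsistency is real and rests on the text alone. Its expected effect on the trial result is very small. For an exposed subject, the chance of Cavg below 500 ng/mL rises from 0.1-2.8% to about 15-17% (6-28% over the 90% CI of the ratio), assuming carry-over to IV dosing and an unchanged CV. One such subject among 20 evaluable moves mean Cavg by about 2.5%.

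A reader might infer that the primary result or the planned sample size is in danger. The documents do not support that: the trial is estimation only, and the probability of at least 18 of 20 stays above 90% even with three exposed subjects. The reason to act is consistency and the safety of a rare neutropenic subject. This is a cheap improvement, not a flaw that undermines the design.

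**What to change.** 1. Delete efavirenz from the permitted examples in Section 7.1.1.5.2.
2. Give it its own entry in Table 1. It should not join the existing row, whose washout is 24 hours. The clinical team should set a washout that reflects offset of induction; the documents give no figure for this.
3. Attach a footnote allowing concurrent use only by prior sponsor approval after a documented benefit-risk assessment. The footnote is needed because footnote a bars concurrent use, and exclusions 13-14 and Section 5.8 would otherwise exclude or discontinue the subject. Those provisions should refer to it.
4. Add one line to Section 8.2.3.1: if a Day 10 IV profile is taken under a UDP-G inducer, flag it and report Cavg with and without it. Do not extend this to drugs that act only on oral absorption.

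The cost is one deleted example, one table entry with its footnote and cross-references, and one conditional analysis line. The sample size does not change. The downside is that a rare subject who cannot change antiretroviral therapy may be ineligible or need sponsor approval. Subjects who need rifabutin or phenytoin already face exclusion or discontinuation.

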7.1.1.6 Assignment of Screening Number

All consented subjects will be given a unique screening number that will be used to identify the subject for all procedures that occur prior to randomization or allocation. Each subject will be assigned only one screening number. Screening numbers must not be re-used for different subjects.

Specific details on the screening visit requirements (screening/rescreening) are provided in Section 7.1.5.1.

